7. DISCONTINUATION OF STUDY VACCINATION AND PARTICIPANT DISCONTINUATION/WITHDRAWAL

7.1. Discontinuation of Study Vaccination

Study vaccinations in the double-blind phase will be withheld for the reasons listed below. These participants must not receive any further doses of study vaccine but should remain on study for follow-up with assessments of safety, efficacy, and immunogenicity as indicated in the [Schedules of Activities](#). Additional unscheduled visits may be performed for safety/reactogenicity reasons, if needed. In case of questions, the investigator is encouraged to contact the sponsor.

- Any related AE, worsening of health status or intercurrent illnesses that, in the opinion of the investigator, requires discontinuation from study vaccine
- The participant becomes pregnant
- Unblinding on the participant level that, in the opinion of the sponsor, would compromise the integrity of the data
- Unblinding requested by a study participant in order to receive an authorized/licensed COVID-19 vaccine prior to general unblinding at the time of EUA in the US for the single-dose schedule of Ad26.COV2.S
- Anaphylactic reaction following vaccination, not attributable to causes other than vaccination
- SAE or other potentially life-threatening (Grade 4) event that is determined to be related to study vaccine
- Chronic or recurrent use of systemic corticosteroids and administration of antineoplastic and immunomodulating agents or radiotherapy
- Participant received any experimental medication (including experimental vaccines other than the study vaccine) or received a COVID-19 vaccine or treatment
- Withdrawal of consent to receive further study vaccination
- Participant has a molecularly confirmed SARS-CoV-2 infection based on samples collected within the study (see Section [8.1.2](#))
- Participant previously experienced TTS or HIT.

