All participants that have not discontinued prematurely from the study will have an unblinding visit at which they will be reconsented (Schedule of Activities [1.3.4](#)). This visit is also applicable for participants who were already unblinded during the double-blind phase of the study. If applicable, participants will receive a single dose of Ad26.COV2.S (refer to Section [6.4](#) for participants enrolled in the study during the double-blind phase). At this visit, body temperature, a blood sample, and a nasal swab will be collected from all participants.^a The nasal sample will not be tested locally and will be sent to a central laboratory. A urine pregnancy test (for participants of childbearing potential) will be collected from participants who will be vaccinated with a single dose of Ad26.COV2.S at this visit. If the participant receives a single dose of Ad26.COV2.S at this visit, the above-mentioned procedures will be performed before vaccination.

After vaccination, participants should remain under observation at the study site for at least 15 minutes, except where local regulations require a longer observation period (eg, Belgium), for the presence of any acute reactions after vaccination and will be followed for safety as per

^a The unblinding visit may be combined with the scheduled study visit and procedures that would be duplicated should be done only once. If a blood draw is planned in the scheduled visit no additional blood draw is needed.

Section 8.3. After the unblinding visit, all participants will resume the Schedule of Activities from Section 1.3.3.

The unblinding visit can be done at an already scheduled or an unscheduled visit. Preferably, if a scheduled study visit (Schedule of Activities 1.3.3) is planned within 2 months after the receipt of Amendment 5 local approvals, this unblinding visit may be combined with the planned study visit. If the unblinding visit is combined with a scheduled visit, the procedures of the planned visit should be completed as well with the exception of solicited symptoms collection in the Safety subset (See Section 8.3). If a blood sample is already planned for the scheduled visit, the blood sample of the unblinding visit does not need to be collected.

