The operating characteristics of the study design, statistical methods, study monitoring rules and efficacy evaluations specified in this protocol with the chosen event and sample sizes will be described in a separate modeling and simulation report and will be added to the SAP before the first participant is vaccinated. The SAP will be amended before primary analysis of the double-blind phase. Upon implementation of Protocol Amendment 6, the SAP will be amended before the next scheduled analysis.

To maximize power for the secondary objectives and evaluations in subgroups, any interim testing was abandoned, and a single analysis planned at the end of the double-blind phase.

The overall recruitment target is approximately 30,000 participants. Up to 10% of additional participants may be recruited to partially compensate for increased fraction unblinded prior to unblinding visit and/or increased seroprevalence rates and/or drop-outs.

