The aim is to recruit up to 6,000 participants in the Safety Subset. At the time of writing the Protocol Amendment 4, the target recruitment has not been completed yet. Every effort will be made to reach the target of 6,000 participants, but the final number of participants recruited in the Safety Subset may be less due to unblinding of the participants. After an individual participant has been unblinded, he/she is no longer considered as part of the Safety Subset and no further solicited/unsolicited symptoms that are specific to the Safety Subset will be collected. All other safety reporting requirements applicable for all participants will be maintained (Section [8.3.1](#)).

As of Amendment 7, a passive follow-up approach is adopted: follow-up visits or phone calls by the site at scheduled time points to collect information on any protocol-required safety assessment (see Section [8.3.1](#)).

In addition, SAEs, AEs, and MAAEs related to COVID-19 need to be reported together with the concomitant medications related to these events until study end. Any confirmatory COVID-19 laboratory information should be reported in the eCRF.

Populations for Analysis Sets

For purposes of analysis, the following populations are defined:

Full Analysis Set (FAS): All randomized participants with at least 1 documented study vaccine administration, regardless of the occurrence of protocol deviations and serostatus at enrollment. Analyses of safety will be performed on the FAS. Vaccine efficacy analyses can be repeated using the FAS.

Safety Subset: subset of the FAS for the analysis of solicited and unsolicited AEs.

Per-protocol Efficacy (PP) population^a: Participants in the FAS who receive 2 doses of study vaccine and who are seronegative at the time of 1st vaccination and at Day 71, and who have no other major protocol deviations that were judged to possibly impact the efficacy of the vaccine before unblinding. The PA of VE will be based on the PP population. In the double-blind phase, the PP will be the main analysis population for efficacy analyses.

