9.4.1. Primary Endpoint Evaluation for the Double-blind Phase

The double-blind phase of the study is designed to test the primary hypothesis of VE in the PP population: H0: VE $\leq 30\%$ versus H1: VE $> 30\%$ and will be evaluated at a 2.5% 1-sided significance level.

The primary endpoint will evaluate the first occurrence of molecularly confirmed, moderate to severe/critical COVID-19 according to the case definition in Section 8.1.3.1, with onset at least 14 days after the second vaccination (Day 71) with Ad26.COV2.S versus placebo, in the PP population, including all events from both age groups, with and without comorbidities.

Participants included in the seronegative analysis set are those participants with a negative SARS-CoV-2 serology test result at baseline.

The unblinding visit marks for a participant the end of the double-blind phase, and the start of the open-label phase. For a given participant, all data up to the unblinding visit will be incorporated in the analysis of the double-blind phase.

The minimum criteria that may trigger the primary analysis before at least 90% of participants are unblinded is if the prespecified harm boundaries have been crossed.

A successful primary efficacy conclusion will require establishing the hypothesis H1: VE $> 30\%$ for the primary endpoint.

Exact Poisson regression will be used to estimate the VE and associated CI taking into account the follow-up time. To evaluate the primary null hypothesis: H0: VE $\leq 30\%$ versus H1: VE $> 30\%$ for the primary endpoint, 95% 2-sided confidence interval based on Poisson regression model will be used.

The decision rules for harm are detailed in Section 9.4.1.1.

For any case definition to be considered for classification of COVID-19 cases, there needs to be at least one SARS-CoV-2 positive RT-PCR or molecular test result from any available respiratory tract sample (eg, nasal swab sample, sputum sample, throat swab sample, saliva sample) that is confirmed by the central laboratory. It is possible that not all samples can be confirmed at the time of the analysis. Hence, a sensitivity analysis may be performed using all RT-PCR or molecular test result, regardless of the confirmation by the central laboratory.

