9.9. Analyses for cohort unblinded due to administration of an authorized/licensed COVID-19 vaccine

Investigators may receive requests to unblind study participants who become eligible to receive another authorized/licensed COVID-19 vaccine outside of the study if/when these become available. In these cases, the investigator will discuss with the participant available options and ramifications, including whether they are eligible to receive the Ad26.COV2.S vaccine in the study during the unblinding study visit. If the participant is eligible for an authorized/licensed vaccine according to local immunization guidelines or recommendation and if the participant wishes to proceed with the unblinding to receive another authorized/licensed COVID-19 vaccine outside of the study, the investigator will follow the unblinding procedures. The reason for the unblinding request should be documented.

When unblinding, if it is determined that the participant received the Ad26.COV2.S vaccine (and not placebo), the participant will be informed that there are no data on the safety of receiving 2 different COVID-19 vaccines. Unblinded participants will be asked to continue to be followed in this study in line with the [Schedules of Activities](#). Safety, efficacy and immunogenicity evaluations will be identical for all participants, if applicable and feasible, including participants that are unblinded to obtain an authorized/licensed COVID-19 vaccine and who remain in the study, including participants in the safety subset, if applicable and feasible. All data will be analyzed separately from the point of unblinding for safety, efficacy and immunogenicity, as described in the Statistical Analysis Plan.

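### Sections 9.4.1 and 9.9 assign the follow-up between individual unblinding and the unblinding visit to different analyses, and neither is said to prevail

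*Protocol*

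**What the plan says.** Section 9.4.1 defines the end of the double-blind phase by a visit: "The unblinding visit marks for a participant the end of the double-blind phase, and the start of the open-label phase". It then fixes the data for the primary analysis: "For a given participant, all data up to the unblinding visit will be incorporated in the analysis of the double-blind phase". It states no exception.

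The visit and the breaking of the code are separate events. Section 8.8 says of the unblinding visit: "This visit is also applicable for participants who were already unblinded during the double-blind phase of the study". Section 9.2.1 allows up to 10% extra recruitment to "partially compensate for increased fraction unblinded prior to unblinding visit", and also for seroprevalence and drop-out. Section 7.1 lists, among the reasons for withholding further study doses, "Unblinding requested by a study participant in order to receive an authorized/licensed COVID-19 vaccine prior to general unblinding".

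Section 9.9 deals with participants unblinded to receive an authorised or licensed vaccine elsewhere. They are asked to stay in follow-up, and the rule for their data is: "All data will be analyzed separately from the point of unblinding for safety, efficacy and immunogenicity, as described in the Statistical Analysis Plan".

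**The concern.** Take a participant who received both study doses, was unblinded on request, took another COVID-19 vaccine, and attended the unblinding visit some weeks later. Section 9.4.1 puts those weeks into the primary analysis. Section 9.9 puts them into a separate one. The statements decide which cases and how much person-time enter the test of VE against 30%, so the conflict affects the primary result.

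The two arms would not be affected alike. A participant told that the injections were placebo has the stronger reason to seek another vaccine. If that protected time is counted as placebo time, the placebo rate falls and the estimated VE falls with it. Behaviour and symptom reporting after unblinding would also enter a comparison meant to be blinded, and that influence could act in either direction.

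**Working it through.** **1. The passages side by side**

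| Question | Section 9.4.1 with 8.8 | Section 9.9 |
|---|---|---|
| What ends double-blind data? | The unblinding visit | The point of unblinding |
| Who is covered? | Every participant, including those unblinded earlier | Those unblinded to get an outside vaccine |
| Where does the time between unblinding and visit go? | Double-blind (primary) analysis | Separate analysis |

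The introduction to Section 9 names Sections 9.2 to 9.6 as applying to the double-blind phase and 9.7 to the open-label phase. Section 9.9 is in neither list, and Section 9.4.1 does not refer to it.

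**2. Who could be affected**

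The per-protocol (PP) set requires two doses. Section 7.1 stops further study doses after unblinding on request. Only participants unblinded after the second dose can therefore bring such time into the primary analysis.

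**3. The plan's own power figure (Section 9.2.1)**

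Inputs: 104 events, null VE 30%, assumed VE 65%, 1:1 allocation, one-sided 2.5%. With equal follow-up, the probability that a case is in the vaccine arm is RR/(1 + RR), where RR is the rate ratio:

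- null: 0.70/1.70 = 0.412
- alternative: 0.35/1.35 = 0.259

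The exact binomial test rejects with 32 or fewer vaccine cases out of 104 (exact alpha 0.0187). Power is 0.891, which agrees with the stated figure of approximately 90%.

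**4. Illustration if Section 9.4.1 is applied literally**

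The documents give none of these inputs, so they are assumptions: a fraction f of placebo PP participants takes an outside vaccine, half of their follow-up falls after it, that vaccine is 90% effective, and nobody in the active arm takes one.

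Expected RR = 0.35 / (1 − f × 0.5 × 0.9)

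| f | Expected RR | Expected VE | Power at 104 events |
|---|---|---|---|
| 0% | 0.35/1 = 0.350 | 65.0% | 0.891 |
| 10% | 0.35/0.955 = 0.366 | 63.4% | 0.846 |
| 20% | 0.35/0.910 = 0.385 | 61.5% | 0.787 |
| 30% | 0.35/0.865 = 0.405 | 59.5% | 0.712 |

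**5. A wider range of assumptions**

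Let s be the share of all placebo follow-up that comes after an outside vaccine, and let that vaccine's efficacy be 65% to 95%. Expected RR is 0.35 / (1 − s × efficacy).

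| s | Expected VE | Power at 104 events |
|---|---|---|
| 2% | 64.3–64.5% | 0.87–0.88 |
| 5% | 63.3–63.8% | 0.84–0.86 |
| 10% | 61.3–62.6% | 0.78–0.82 |
| 20% | 56.8–59.8% | 0.60–0.72 |
| 30% | 51.0–56.5% | 0.37–0.59 |

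The two tables use different scales: f = 10% in step 4 corresponds to s = 5% here.

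**6. The same situation with follow-up ended at unblinding**

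Expected VE stays at 65%. Placebo time falls to 1 − s, so expected events are 104 × ((1 − s) + 0.35)/1.35: about 102, 100, 96, 89 and 81 for s of 2%, 5%, 10%, 20% and 30%. The exact test, adjusted for the unequal follow-up, has power of about 0.90, 0.89, 0.90, 0.85 and 0.86. The unevenness comes from the discreteness of the exact test.

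**The case against.** The strongest reply is that Section 9.9 is the specific rule for this cohort and Section 9.4.1 the general one, so 9.9 should be read as the exception. The extra recruitment in Section 9.2.1 fits that reading, since compensation makes most sense if early-unblinded follow-up is lost to the analysis. This stands as a plausible account of the intention. It does not remove the conflict, because Section 9.4.1 is unqualified and no text shown gives 9.9 priority.

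Two stronger readings are tempting and are not supported:

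- **That outside-vaccinated placebo time does enter the primary analysis.** It does so only if Section 9.4.1 is applied as written. If 9.9 governs, the time of that cohort is kept out.
- **That other cases, such as an outside vaccine taken without unblinding, fall under Section 9.4.1 alone.** The concomitant-therapy text before Section 6.11 disallows other coronavirus vaccines except under Sections 6.3 and 6.8. The PP definition keeps participants "who have no other major protocol deviations that were judged to possibly impact the efficacy of the vaccine before unblinding", and the closing words may describe when the judgement is made rather than when the deviation occurred. Such a vaccine may therefore lead to exclusion. Sections 6.3, 6.4 and 6.8 are in the part of the protocol not available for this check.

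It is also fair to say that the SAP, not at hand here, may contain a censoring rule. The point is not missing detail, though: two statements in the protocol disagree. Finally, the power figures are illustrative, because Section 9.1 triggers the analysis by the proportion unblinded and not by 104 events. The 10% in Section 9.2.1 also covers seroprevalence and drop-out, so it is not evidence that 10% would be affected.

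**Conclusion.** The protocol contradicts itself on which data of early-unblinded participants belong to the primary analysis, and this needs to be reconciled. Followed literally, Section 9.4.1 would bias VE towards the 30% null. The direction is conservative for the success claim, so the loss is in accuracy and power, and type I error is not inflated from this source.

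The size cannot be derived from the documents. With a 90% effective outside vaccine covering half of the affected follow-up and no uptake in the active arm, VE falls from 65% to about 63% with 10% of placebo participants affected and to about 60% with 30%. The contradiction itself depends on none of these assumptions.

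**What to change.** In Section 9.4.1, state that double-blind efficacy follow-up for the primary analysis ends at the earliest of the participant's actual unblinding, receipt of a COVID-19 vaccine outside the study, and the unblinding visit. Cross-refer to Section 9.9, and have 9.9 point back to the same rule. Present the analysis up to the unblinding visit as a sensitivity analysis.

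The cost is wording in two sections and a small loss of events and person-time. The protocol already requires the name and dates of any outside COVID-19 vaccine in the eCRF. Ending follow-up at any actual unblinding goes further than Section 9.9, which covers only unblinding to obtain another vaccine. The sensitivity analysis shows whether that choice affects the result.

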9.2. Sample Size Determination

9.2.1. Efficacy (Total Sample Size)

For the double-blind phase, the sample size is determined using the following assumptions:

- a VE for molecularly confirmed, moderate to severe/critical SARS-CoV-2 infection of 65%.
- type 1 error rate $\alpha = 2.5\%$ to evaluate VE of the vaccine regimen.
- a randomization ratio of 1:1 for active versus placebo

Events are defined as first occurrence of molecularly confirmed, moderate to severe/critical COVID-19 according to the case definition in Section 8.1.3.1 in the PP population at least 14 days after the second vaccination with study vaccine (Day 71).

Under the assumptions above, a total of 104 events will provide approximately 90% power to reject the null hypothesis of $H_0: VE \leq 30\%$, according to the primary endpoint case definition of moderate to severe/critical COVID-19 (Section 8.1.3.1).

If the primary hypothesis testing is successful, secondary objectives will be evaluated against a null hypothesis employing a lower limit $VE > 0\%$. The method to perform hypothesis testing of primary and secondary objectives preserving the FWER will be specified in the SAP. The FWER will be controlled at 2.5%.

Sample Size Justification

Based on the variations in seroprevalence, degree of social distancing and use of personal protective equipment, it is not feasible to estimate the incidence rates that can be attained at the time of the start of this study. It is also unknown which local regulations (eg, potential lockdowns) will be in effect at that time.

The sample size is approximately 15,000/group (approximately 30,000 in total) and is determined based on estimated annualized incidence rate of moderate to severe/critical COVID-19 of 1% to 4% at the start of the study.

Assuming 2 months of recruitment and 10% seroprevalence, the selected sample size will have a high probability (approximately 90%) to have reached an efficacy signal within 15 months after first participant vaccinated for an assumed $VE \geq 65\%$ under an assumed incidence of 1.4% in Month 1-3, and waning of incidence thereafter, eg, 50% reduction at Month 4 (0.70% annualized) followed by further reduction to 0.58%.

With higher incidences at the start of the study, the timelines to efficacy will shorten.

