The primary efficacy analysis will pool data across populations (with and without comorbidities) to evaluate the primary and secondary objectives. In addition, these will be supplemented with a subgroup analysis for age and comorbidities employing a descriptive summary including 95% confidence intervals to describe the VE in each subpopulation.

In addition, to assess potential time-effects of VE, the Kaplan-Meier method will be used to plot the estimated cumulative incidence rates over time for the vaccine and placebo groups. This

method will be used to estimate cumulative VE over time, defined as $[(1 \text{ minus ratio (vaccine/placebo) of cumulative incidence by time } t) \times 100\%]$.

Furthermore, VE will be evaluated in seronegative participants, counting primary endpoints since onset after the first vaccination.

Of note, the data may be pooled with data of other ongoing efficacy studies in support of health authorities' interactions.

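### Time-effects of VE in the double-blind phase are assessed only through cumulative VE, which damps and delays any sign of waning and gives no estimate for a later period

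*Protocol*

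**What the plan says.** Section 9.4.1 gives a purpose and a method together: "to assess potential time-effects of VE, the Kaplan-Meier method will be used to plot the estimated cumulative incidence rates" for the vaccine and placebo groups. It adds that this "method will be used to estimate cumulative VE over time" and supplies the formula, 1 minus the vaccine/placebo ratio of cumulative incidence by time t.

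The primary estimate is a single figure over all blinded follow-up: "Exact Poisson regression will be used to estimate the VE and associated CI taking into account the follow-up time". In Section 9.4.2, the analyses of any infection, of asymptomatic infection and of cases needing medical intervention also use Poisson regression over follow-up. Section 9.4.1 adds an analysis that counts cases from the first vaccination, which only moves the start of the window. Section 9.7.4 mentions duration of protection for booster vaccinations in the open-label phase. In the text available, no double-blind analysis gives VE for a stated period after Day 71.

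Section 9.4 describes itself as a summary and refers to the SAP for technical detail. The SAP and the first part of the protocol, including the objectives in Section 3, were not available for this check.

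**The concern.** The stated aim is to see whether VE changes with time. The chosen measure answers a different question: what share of cases has been averted so far. Once early protection is in the average it stays there, so a decline shows up late and reduced, and current VE cannot be read off the curve. The primary Poisson estimate is also an average over follow-up and cannot fill the gap.

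What is at stake is the description of how long protection from the 2-dose regimen lasts. If VE wanes, cumulative VE at a late time exceeds VE at that time, and nothing named beside it tells the reader by how much.

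**Working it through.** **The plan's own figure.** The time-effects text states no number. The nearest planning figure is in Section 9.2.1: "a total of 104 events will provide approximately 90% power to reject the null hypothesis", for VE 65% against a null of 30%, one-sided 2.5%, 1:1 allocation. Conditional on 104 cases, the vaccine-arm share is 0.70/1.70 = 0.412 under the null and 0.35/1.35 = 0.259 under the alternative. Rejecting at 32 or fewer vaccine cases gives exact one-sided alpha 0.0187 and power 0.891. The figure is reproduced, and nothing below changes it.

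**Inputs for the time-effects check.**
- From Section 9.2.1: annualized incidence 1.4% in months 1-3, 0.70% in month 4, then 0.58%; 15,000 per arm; 10% seroprevalence.
- Assumed: the waning patterns, since the protocol gives none; flat and rising incidence as alternatives; no dropout or unblinding. The incidence pattern is applied to months at risk as an illustration.

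**Formula.** With placebo hazard λ(u), cumulative VE(t) = 1 − [1 − exp(−Hv(t))]/[1 − exp(−Hp(t))], where Hp = ∫λ(u)du and Hv = ∫λ(u)(1 − VE(u))du. For rare events this is close to ∫λ(u)VE(u)du / ∫λ(u)du, the incidence-weighted mean of past VE.

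**Step loss: VE 65% for 3 months, then 0%.** Weights are annualized % × months.

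| Incidence | Weight, months 0-3 | Weight, months 3-6 | Cumulative VE, month 4 | Cumulative VE, month 6 | Current VE |
|---|---|---|---|---|---|
| Protocol (1.4, 0.70, 0.58) | 4.20 | 0.70 + 1.16 = 1.86 | 0.65 × 4.20/4.90 = 56% | 0.65 × 4.20/6.06 = 45% | 0% |
| Flat 1.4 | 4.20 | 4.20 | 0.65 × 3/4 = 49% | 0.65 × 3/6 = 32% | 0% |
| Rising 0.58 to 1.4 | 1.74 | 4.20 | 0.65 × 1.74/3.14 = 36% | 0.65 × 1.74/5.94 = 19% | 0% |

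(By the full formula the flat month-6 value is 32.4%.) Falling incidence makes the lag larger, because early, well-protected time carries most of the cases.

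**Gradual loss: VE 80% falling linearly to 0% over 12 months.** At month 6 current VE is 40%, and cumulative VE is 64% (protocol incidence), 60% (flat) or 56% (rising). At month 12 current VE is 0%, and cumulative VE is 48%, 40% or 35%.

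**What broad intervals would show.** Step loss, protocol incidence, 15,000 × 0.90 = 13,500 seronegative participants per arm; Wald CIs on the log rate ratio:
- Months 0-3: 13,500 × 0.042/12 = 47 placebo and 0.35 × 47.25 = 17 vaccine cases. VE 65% (95% CI 39% to 80%).
- Months 3-6: 13,500 × 0.0186/12 = 21 in each arm. VE 0% (−83% to 45%).
- Months 0-6 pooled, which is cumulative VE at month 6: 68 and 37 cases. VE 45% (18% to 63%).

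**Why not 28-day intervals.** At 0.70% annualized, 13,500 × 0.0070 × 28/365 = 7 placebo cases. At 7 versus 7 the standard error of the log ratio is √(2/7) = 0.535, so the CI for VE is about −185% to 65%.

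**The case against.** The protocol labels the quantity correctly as cumulative and gives its formula; it never calls it current VE. The measure does fall with waning: in the flat step case it goes from 65% to 49% to 32%. The two Kaplan-Meier curves are also plotted, so parallel curves would show lost protection, and the ratio of increments between two times recovers interval VE. All of this stands. A reader might infer that the plan hides waning or would report lost protection as if it were present. The text does not support that; damped and delayed is the accurate description.

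A reader might also infer that a booster decision for the 2-dose regimen rests on this curve. Section 8.9 makes participants who had two Ad26.COV2.S doses ineligible for the booster, so the document gives no such link.

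VE by interval is the kind of supportive table that often sits in an SAP, and the SAP may contain one. The point is therefore limited to what Section 9.4.1 itself fixes: it names the purpose and ties it to cumulative VE alone.

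Late data will be sparse. Blinded follow-up ends at each participant's unblinding visit, and how many reach month 6 after Day 71 is not established. That is a fair argument against fine intervals. It does not favour an average in place of an imprecise estimate that shows its own uncertainty.

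Finally, Section 9.4 describes the primary-analysis SAP as already final, so the addition may come after the data have been seen.

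**Conclusion.** The concern holds as a modest, cheap improvement. Cumulative VE is a legitimate descriptive display, but used alone it is a poor measure of time-effects: it damps and delays waning and gives no estimate or CI for a later period. The gap can be large. In the step illustration it is 45 percentage points at month 6 under the protocol's incidence pattern, 32 under flat incidence and 19 under rising incidence. These sizes depend on assumed waning and on undisturbed blinded follow-up. With rising incidence and longer follow-up the residual shrinks, to 8% at month 12 in the same scenario. The primary hypothesis test, its Poisson estimate and the event calculation are not affected.

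**What to change.** In Section 9.4.1, keep the Kaplan-Meier curves and cumulative VE and call them descriptive. Name one time-effects analysis, with 95% CIs:
- VE (1 minus the incidence-rate ratio) in a few prespecified intervals since Day 71, for example about 2 to 3 months each rather than 28 days; or
- a Cox or piecewise model with a time-varying vaccine effect.

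If the SAP already contains such an analysis, refer to it in Section 9.4.1 as the time-effects analysis. If the double-blind data have already been analyzed, label the addition as made afterwards.

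The cost is one extra table or figure. Late-interval CIs will be wide, and unblinding will widen them further; the interval estimates should be presented with that caution.
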